RESEARCH PROTOCOL

Date	December 27, 2022
Title	Evaluating the use of pre-epidural placement of SCDs to prevent
	hypotension
Principal Investigator	[name], MSN, RN, APRN, FNP-C
Sub-Investigators	[name], MSN, RNC-OB, C-EFM; [name], MSN, RNC-
	OB, C-EFM; [name], BSN, RNC-OB, C-EFM; [name], BSN, RNC-OB, C-EFM
Research Specialist	[name], RN, CPN
Department	Bethesda North Hospital, Labor & Delivery
Hatton #	21-020

Purpose of Study

Women given epidural analgesic during labor often experience hypotension. When this happens, it typically occurs in the first 30-60 minutes after epidural placement. This maternal low blood pressure can result in decrease perfusion of the placenta and ultimately impact blood flow to the infant which is seen through decreases in the infant's heart rate.

Hypothesis or Research Question

- Hypothesis 1: Laboring women who receive epidural analgesia and use sequential compression devices (SCDs) will experience a lower incidence of hypotension compared to laboring women who receive epidural analgesia and do not use SCDs.
 - *hypotension is defined as SBP < 90 mmHg or an SBP decreases more than 20% from baseline
- Hypothesis 2: Infants of laboring women who receive epidural analgesia and use SCDs will experience a lower incidence of Category 2 tracings compared to laboring women who receive epidural analgesia and do not use SCDs.

Background

Women given epidural analgesic during labor can experience hypotension. Hypotension is defined as a systolic blood pressure of less than 90 mm Hg or diastolic blood pressure of less than 60 mm Hg. Maternal physiologic changes such as increased blood volume will have an impact on the circulation system; low maternal blood pressure can result in decreased perfusion of the placenta and ultimately impact blood flow to the fetus, which is seen via a category II or III fetal heart rate monitoring. While hypotension may not cause problems for some non-pregnant women, the fetus in utero is used to and dependent on a certain blood pressure threshold.

When hypotension related to epidural placement, this can occur within 15-60 minutes after placement. The purpose of this study is to build upon this preliminary work and to use a randomized controlled trial to examine the effectiveness of SCDs in preventing hypotension among a larger sample of laboring women who receive an epidural analgesia.

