- Blood pressure on admission SBP>160 or DBP>110
- Fetal heart rate abnormalities before epidural

Sample Size Determination: A power analysis was conducted using the primary outcome variable, maternal hypotension, with an expected difference similar to that found in the Peyronnet and colleagues' (2017) study (3.23% vs. 23.3%) (0.3), power of 0.8, and level of significance 0.05. It was determined that 44 patients would be needed in each group, for a total sample size of 88 patients. To allow us to also examine the impact on occurrence of infant Category 2 tracings and to allow for the possibility of removing participants from the final analysis due to missing data, we plan to enroll 120 patients (60 in each group).

• Data Collection

Before the study begins, information about the study will be provided to the providers. Providers who agree with involvement of their patients will be provided a hand-out about the study to give to their patients during prenatal visits and asked to mention to their patients that they may be approached about involvement of the study when they are admitted. The nurses on the L&D unit will be provided with education about the study purpose, exclusion criteria, and procedures. All nurses on the L&D unit have received training in the proper use of SCDs clinically. However, to validate and reinforce this knowledge, the nurses on the L&D unit will be provided education on proper measurement to determine boot size for SCDs and proper boot placement and SCD use. Nurses will be instructed to call a member of the study team immediately if any safety concerns occur related to the SCDs.

When a patient who meets the inclusion/exclusion criteria is admitted, a nurse will describe the study, answer any questions the patient has, and if the patient wants to enroll in the study, the study team nurse will review the information consent form. After the patient provides written informed consent, the nurse will remove the next envelope out of a box of prefilled and sealed opaque envelopes. The envelope will provide the Subject ID number to be used on all study-related documentation and the study Arm that the patient has been randomized to, either:

- 1. SCD Group + Fluid Bolus
- 2. Fluid Bolus Group (no SCD)

These envelopes will be filled using a computerized simple random number generator (1:1 randomization) prior to the start of the study.

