Hypothesis 1: Laboring women who receive epidural analgesia and use SCDs will experience a lower incidence of hypotension compared to laboring women who receive epidural analgesia and do not use SCDs.

To compare the effects of the SCDs, a Chi Square test will be used to compare occurrence of maternal hypotension for patients who used SCDs to patients who did not use SCDs. A level of significance of α =0.05 will be used.

Hypothesis 2: Infants of laboring women who receive epidural analgesia and use SCDs will experience a lower incidence of Category 2 tracings compared to laboring women who receive epidural analgesia and do not use SCDs.

To compare the effects of the SCDs, a Chi Square test will be used to compare occurrence of Category 2 tracings of infants of patients who used SCDs to infants of patients who did not use SCDs. A level of significance of α =0.05 will be used.

Interim data analysis will occur (1) once approximately 1/3 of the participants have been enrolled in each group and (2) once approximately 2/3 of the participants have been

enrolled in each group. If interim calculations at time (1) or time (2) note a significant difference between groups in maternal hypotension or frequency of category 2 tracings, data collection will be completed at that time and final analysis will be completed.

Ethical Considerations

• Informed consent

All study staff will complete CITI training. A study staff member will meet with potentially eligible patients and describe the study and answer any questions. If the patient is interested and meets all the inclusion/exclusion criteria, the study staff will review the *Informed Consent Form* and obtain written informed consent. Patients will receive a copy of their signed Informed Consent form.

Informed Consent forms will be stored in a locked room that only staff will have access to. After the study closes, the signed Informed Consent forms will be boxed and sent to off-site storage and securely stored until the infant turns 21 years of age. At that time, the hard copy forms will be shredded.

• Privacy information

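### Three looks at an unadjusted 0.05 roughly double the false-positive risk for hypotension, to about 10–11% instead of 5%

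*Combined protocol and SAP*

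**What the plan says.** Under Statistical Analysis, Hypothesis 1 is assessed as follows: "a Chi Square test will be used to compare occurrence of maternal hypotension". Hypothesis 2 is assessed the same way for Category 2 tracings. For each the plan adds: "A level of significance of α =0.05 will be used". Whether the chi-square carries a continuity correction is not stated.

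The last paragraph of that section sets the interim looks: "Interim data analysis will occur (1) once approximately 1/3 of the participants have been enrolled in each group", and again at about two thirds. The trigger is: "If interim calculations at time (1) or time (2) note a significant difference between groups in maternal hypotension or frequency of category 2 tracings". The consequence is: "data collection will be completed at that time and final analysis will be completed". No boundary, alpha-spending function or adjusted final level appears anywhere in the document.

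Sample Size Determination identifies the primary outcome: "A power analysis was conducted using the primary outcome variable, maternal hypotension". Category 2 tracings enter only as part of the reason for enrolling 120 rather than 88: "To allow us to also examine the impact on occurrence of infant Category 2 tracings and to allow for the possibility of removing participants".

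**The concern.** A test at 0.05 has a 5% false-positive rate only if it is done once. Here the hypotension test can be done three times, and the trial ends at the first significant result, so each look adds its own chance of a false positive. This is a binding efficacy rule, separate from the safety pause described under Data Collection.

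Three things are at stake:

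- A claim for a new use of the device would carry about twice the stated risk of being false.
- Trials that stop at the first look would tend to exaggerate the benefit.
- Category 2 could close the trial while the primary outcome was still unresolved.

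**Working it through.** **1. The plan's own figure.** Inputs from Sample Size Determination: 3.23% vs 23.3%, power 0.8, level 0.05. With p̄ = (0.0323 + 0.233)/2 = 0.13265:

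n = [1.96·√(2p̄(1−p̄)) + 0.8416·√(p₁(1−p₁) + p₂(1−p₂))]² / (p₂−p₁)² = (0.940 + 0.386)² / 0.2007² ≈ 43.6, so 44 per arm.

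This matches the plan. The two-sided formula with continuity correction gives 54, so the plan was sized for an uncorrected two-sided test.

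**2. The design as written.** One third, two thirds and all of 60 per arm give looks at 20, 40 and 60. With x₁ and x₂ events in arms of n, the statistic is X² = 2n(x₁−x₂)² / [(x₁+x₂)(2n−x₁−x₂)]. The trial stops at the first X² above 3.841.

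**3. Error for hypotension if hypotension alone governs stopping.** This is an exact enumeration of both arms' event counts, with no true difference. The null rates are assumptions, because the plan gives none. If SCDs do nothing, both arms share the untreated rate, and the plan's only figure for that is 23.3%.

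| Common rate | Three looks | One test at 60 | Ratio |
|---|---|---|---|
| 3% | 4.53% | 3.55% | 1.3 |
| 5% | 7.59% | 4.59% | 1.7 |
| 10% | 10.63% | 5.05% | 2.1 |
| 15% | 10.78% | 4.69% | 2.3 |
| 20% | 10.88% | 4.99% | 2.2 |
| 23.3% | 10.99% | 5.18% | 2.1 |
| 30% | 11.09% | 5.25% | 2.1 |

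- The large-sample value for three equally spaced looks at z = 1.96 is 10.7%.
- Look 1 alone spends 3.9–5.3% at rates of 10–30%.
- In the direction of benefit only, the three-look error is 5.3–5.5%, against about 2.5%.
- Moving the looks by 3 patients per arm gives 10.2–11.3%.
- With a Yates correction the three-look error is 3.1–6.0%, against 2.2–3.1% for one test.

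**4. The either-outcome rule.** 100,000 simulated trials per scenario; assumed Category 2 rate 20–40%, correlation between the outcomes 0 to 0.70, hypotension rate 10–30%.

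- Hypotension error is 10.0–10.8%. It is slightly lower than in step 3 because Category 2 sometimes ends the trial first.
- Category 2 alone ends the trial early in about 6–8% of trials when SCDs do nothing.
- With the planned hypotension effect and no Category 2 effect, Category 2 alone does so in about 3%. Hypotension power falls from 95.3% to 92.5%.

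**5. Under the planned effect (3.23% vs 23.3%), hypotension-only stopping.** The current rule stops 49.1% of trials at look 1 and 84.6% by look 2. Mean enrolment is 40(0.491) + 80(0.846−0.491) + 120(1−0.846) ≈ 67. Trials stopping at look 1 report a mean difference of 28 points, against a true 20.

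**6. With an O'Brien-Fleming boundary (z = 3.471, 2.454, 2.004).** Error is 4.7–5.2% at null rates of 10–30%. Stopping is 0.45% at look 1 and 64.9% by look 2. Mean enrolment is 40(0.0045) + 80(0.649−0.0045) + 120(1−0.649) ≈ 94. Power is 94% with 60 evaluable per arm and 85% with 44, against 94% and 87% for a single test.

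**The case against.** **The interim level is inferred.** The interim sentence requires a significant difference but names no level. That is true, but 0.05 is the only level given and is the natural reading. If another level was intended, the plan has to state it.

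**The doubling depends on the test variant and the event rate.** With Yates the error stays near 5%, and at a 3% event rate it does not exceed 5%. Both conditions stand. However, the plan mentions no correction, its sample size matches the uncorrected formula, and its comparison rate of 23.3% lies inside the 10–30% range. Even with Yates the looks raise the error of that test.

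**The 28-point figure is not specific to unadjusted looks.** Any early-stopping rule overestimates among the trials it stops early. Under the O'Brien-Fleming boundary the rare look-1 stops would report about 52 points. This stands: the boundary makes such stops very uncommon but does not remove the bias.

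**Category 2 is a separate hypothesis and does little harm.** The power loss is indeed small, and nothing in the plan commits it to a joint error rate. For a reader who wants one, the chance of a false positive on either outcome is about 18–21%, against 8–10% for single tests, under the assumptions of step 4. It falls to 14.7% if the test statistics correlate at 0.9. The Background gives reason to expect positive correlation, since it says "low maternal blood pressure can result in decreased perfusion of the placenta and ultimately impact blood flow to the fetus". The main finding does not rest on the joint rate.

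**Conclusion.** The concern holds. As written, the hypotension comparison does not have a 5% false-positive rate. It is about 10–11%, roughly double, assuming an uncorrected chi-square, 0.05 applied at each of three looks near 20, 40 and 60 per arm, and a common event rate of 10–30%. The error in the direction of benefit also roughly doubles. Letting Category 2 stop the trial is a lesser fault: its cost in power is small, but an outcome with no power calculation should not be able to close the trial before the primary outcome is settled.

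**What to change.** - State a three-look boundary for hypotension only and specify the uncorrected chi-square. One example is O'Brien-Fleming with nominal two-sided p of about 0.0005, 0.014 and 0.045, or an equivalent alpha-spending function if look times vary. A constant level of 0.0221 at each look would also work (error 3.8–5.0% at rates of 10–30%).
- Remove Category 2 tracings from the stopping rule and test them once, at 0.05, when data collection ends.
- Preferably, test Category 2 only if hypotension has crossed its boundary. This is a choice that the hypotension boundary does not need. With it, two-sided Category 2 error was at most 5.1% in the scenarios examined. In the benefit direction it can reach 2.9–3.5%, against 2.5%, when the test statistics correlate at 0.5–0.9.
- If an unadjusted look has already been made, report it with the resulting error. The document is dated December 2022 and its timeline lists a 2021 start, but it does not say whether any look has occurred. Applying the O'Brien-Fleming levels to the remaining looks leaves about 7.5–9% after one unadjusted look and 10.1–10.6% after two (null rates 10–30%); later boundaries cannot restore 5%.

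**Cost.** The document change is wording only, and the maximum stays at 120. The operational cost is later stopping: under the planned effect, mean enrolment rises from about 67 to about 94, and look-1 stopping falls from 49% to under 1%. If Yates were used with this boundary, power would be 88% with 60 per arm and 73% with 44, which is why the variant should be stated.

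### A significant interim difference in either hypotension or Category 2 tracings ends the whole trial, so the secondary question can cut short the primary one, and Hypothesis 2 may never reach the enlarged sample of 120

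*Combined protocol and SAP*

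**What the plan says.** Sample Size Determination fixes the order of the outcomes: "A power analysis was conducted using the primary outcome variable, maternal hypotension". It finds 44 women per group, 88 in total. It then raises enrolment to 120 (60 per group) for two reasons. One is missing data. The other is "To allow us to also examine the impact on occurrence of infant Category 2 tracings".

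The interim paragraph at the end of Statistical Analysis plans a first look "once approximately 1/3 of the participants have been enrolled in each group" and a second at about two-thirds. With 60 per group these fall at about 20 and 40 per arm, or 40 and 80 women. If the calculations at either look show a significant "difference between groups in maternal hypotension or frequency of category 2 tracings, data collection will be completed at that time", and the final analysis follows.

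The rule gives hypotension no precedence over Category 2 tracings. It does not let the other outcome continue, and it does not say how that outcome is reported after an early stop. Each hypothesis is to be tested by chi-square at 0.05. No separate interim level is given.

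**The concern.** The sample was enlarged partly for Hypothesis 2, yet the rule can end the trial at one-third or two-thirds of that sample. Two consequences follow.

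- If hypotension differs as the plan expects, Hypothesis 2 will often be tested on 20 or 40 women per arm. Both stopping points are below even the 88 computed for hypotension.
- If Category 2 tracings cross the threshold first, the primary question is closed while still unanswered, on the strength of an outcome for which the plan states no expected rates and no power.

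This point concerns how long the trial runs against its two objectives. The type I error of repeated looks is a separate matter.

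**Working it through.** **Inputs from the plan.** Hypotension 3.23% (SCD) vs 23.3% (control); power 0.8; alpha 0.05; 1:1 allocation; 120 women; looks at about 1/3 and 2/3; chi-square test.

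**Assumptions.** "Significant" is read as p < 0.05 at each look. Looks are at 20, 40 and 60 per arm. Category 2 rates of 15% (SCD) vs 30% (control) are illustrative. Figures in parentheses use the continuity-corrected chi-square, since the plan does not say which form applies.

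**1. The plan's own figure.** For two proportions with pooled variance, two-sided and without continuity correction:

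n = [1.96·√(2·p̄·q̄) + 0.8416·√(p₁q₁ + p₂q₂)]² / (p₁ − p₂)²

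Here p̄ = (0.233 + 0.0323)/2 = 0.13265, so √(2 × 0.13265 × 0.86735) = 0.4797. Also √(0.1787 + 0.0313) = 0.4582, and p₁ − p₂ = 0.2007.

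n = (0.9402 + 0.3856)² / 0.04028 = 43.6, rounded up to 44 per arm. The stated 44 reproduces.

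**2. Early stopping on hypotension alone** (exact binomial enumeration at 20 and 40 per arm).

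| Hypotension, control vs SCD | Stop at 40 women | Stop by 80 women |
|---|---|---|
| 23.3% vs 3.23% (the plan) | 49% (22%) | 85% (67%) |
| 23.3% vs 8% | 26% (12%) | 53% (35%) |
| 23.3% vs 11.65% | 16% (7%) | 33% (19%) |
| 23.3% vs 23.3% | 5% (2%) | 8% (4%) |

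In the first row, uncorrected, 49.1% at look 1 plus 35.5% at look 2 gives 84.6%. Fisher's exact test gives 71% by 80 women.

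**3. Sensitivity to the interim level**, at the plan's rates. O'Brien-Fleming-type limits (z = 3.47 and 2.45) give 65% (43%) by 80 women, with almost none at 40. A fixed limit of z = 3.29 gives about 21% (8%).

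**4. Cost to Hypothesis 2** (simulation; Category 2 at 15% vs 30%, outcomes independent, stopping on hypotension only).

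- At the full 120: power 51% (42%).
- Averaged over all trials when hypotension can stop the trial: 31% (28%).
- Among trials that hypotension ends early: 27% (21%).

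**5. Cost to the primary question** (same rates; stopping on either outcome).

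| | Outcomes independent | Latent correlation 0.5 |
|---|---|---|
| Trial ended by Category 2 alone, hypotension not significant at that look | 14% (15%) | 10% (11%) |
| Chance of a significant hypotension result, with the Category 2 trigger | 84% (79%) | 87% (81%) |
| The same, without the trigger | 95% (90%) | 95% (90%) |

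With both triggers and independent outcomes, 91% of trials (76%) stop before 120, and mean enrolment is about 60 (77).

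**The case against.** **Stopping once the primary question is answered is a recognised design choice.** That stands. A stop on hypotension is not an error in itself. What lacks support is a stop on the secondary question while the primary one is open, and the silence on Hypothesis 2 after an early stop.

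**The likelihood of early stopping depends on the planned effect and the interim level.** This also stands. The 3.23% vs 23.3% comes from a comparison with historical controls. At half the control rate (23.3% vs 11.65%), hypotension alone stops about 33% of trials. Stricter interim limits would also make early stops rarer, so a remedy for repeated testing would ease part of this problem. It would still leave Category 2 tracings able to end the primary comparison.

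**The outcomes are not independent.** The Background links maternal hypotension to fetal tracings. Positive correlation shrinks the loss to the primary question, as step 5 shows, but does not remove it.

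**A reader might infer that a null result on Hypothesis 2 is uninterpretable because of early stopping.** The documents do not support that. They promise no power for Hypothesis 2, only that its outcome will be examined, and the increase to 120 also covers missing data. Under the assumed rates, power at the full 120 is itself only 51% (42%), so a null result there would be weak too. Early stopping makes a weak test weaker.

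**A reader might also infer that enrolment must run to 120, with looks for harm only.** Nothing in the plan requires this. It would give up early stopping for benefit, which is a trade-off for the sponsor.

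**Conclusion.** The concern holds in a limited form. The rule ends data collection for both hypotheses when either one is significant, which conflicts with the order of the outcomes and with part of the stated reason for 120 women.

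At the plan's own effect and 0.05 at each look, the trial more likely than not stops by 80 women on hypotension alone. That is a conditional statement and does not carry over to smaller effects.

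The sizes given for Hypothesis 2, and for the loss of roughly 8 to 12 percentage points in the chance of a significant primary result, rest on assumed Category 2 rates of 15% vs 30%. The direction does not depend on those rates: a second trigger can only bring the end of the trial forward, and an earlier end leaves fewer women for the other question.

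**What to change.** Make two changes to the interim paragraph.

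1. Delete the clause that makes a difference in Category 2 tracings a ground for ending data collection, so that only the primary outcome, maternal hypotension, can end it for benefit.
2. Add a sentence that if the trial stops early on hypotension, Hypothesis 2 will be reported as an estimated difference with its 95% confidence interval, not as a confirmatory test.

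The cost is that the trial may run longer, though within the 120 women and 3 months of data collection already planned. Because the present rule has no direction, the deletion also removes a stop for an excess of Category 2 tracings in the SCD arm. If the sponsor intends one, it needs its own sentence. The enrolment pause for SCD safety concerns under Data Collection is unaffected.
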